**Title:**

Patient Education Bundle vs. Nurses feedback and Coaching to Prevent Missed Doses of Venous Thromboembolism (VTE) prophylaxis: A crossover, cluster randomized controlled trial

**Acronym:**

ENACT (Patient Education Bundle vs. Nurses FeedbAck and Coaching Trial)

**Overview**

VTE associated harm is underappreciated among hospitalized patients and may be associated with missed doses of VTE prophylaxis medications. In order to ensure best practices, and administer a defect-free VTE prevention nurses must understand and educate patients on the importance of the VTE prophylaxis. We propose to conduct a randomized trial comparing the effect of a validated, real-time patient education bundle (PEB), to a program of nurse feedback and coaching (NFC) provided by nurse leaders.

**Background**

Missed doses of prescribed Venous Thromboembolism (VTE) pharmacologic prophylaxis is significant problem. Data on patients admitted to The Johns Hopkins Hospital found approximately 12% of prescribed doses of pharmacologic VTE prophylaxis were not administered. There were several reasons for these missed doses. The leading reason (nearly 60% of missed doses) was patient or family member refusal for any reason.

Based on data collected by the Maryland Health Services Cost Review Commission (HSCRC) in the Maryland hospital-acquired conditions (MHAC) program, during 2011 half of patients who developed confirmed VTE at The Johns Hopkins Hospital were not administered one or more doses of prescribed VTE prophylaxis. These data indicate that missed or refused doses of VTE prophylaxis represent a significant and under-recognized contributor to sub-optimal VTE prophylaxis that will erode the beneficial impact of current efforts to improve rates of VTE prophylaxis ordering by physicians.

As part of a Patient-Centered Outcomes Research Institute (PCORI)-funded project, the investigators have developed a registry of missed doses of VTE prophylaxis that includes data on missed doses of VTE prophylaxis.

**Primary hypothesis**

Both interventions (PEB and NFC) will improve medication administration (as measured by missed doses)

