## Nurse satisfaction

### **Analysis plan**

We will have a blinded biostatistician team perform all analyses.

We will use the intention-to-treat (ITT) approach.

We will compare outcomes across intervention periods.

We will compare outcomes based upon randomized floor.

We will use multiple outputation to reduce the levels of hierarchical structure to the floor and nurse level by randomly selecting one VTE prophylaxis dose per patient and reiterate the procedure 1000 times to bootstrap the p values for the comparisons. This methodology will be similar that taken previously in our prior work in similar circumstances.

We will adjust by floor type (medicine vs. surgery) and patient level characteristics (race, sex, age, insurance) when calculating proportions and risk of missed doses.

We will conduct a sensitivity analysis (excluding floors where prior intervention occurred).

Check for differential effect that may eliminate biases in pre-implementation data (by race, age, sex)

PRE-TRIAL (6 MONTHS)	PERIOD I (3 MONTHS)	PERIOD II (3 MONTHS)	POST-TRIAL (3 MONTHS)	
RANDOMIZATION	<pre> graph LR     A[RANDOMIZATION] --> B[PEB]     A --> C[NFC]     B --> D[NFC+PEB]     B --> E[PEB+NFC]     C --> D     C --> E     D --> F[POST-TRIAL PERIOD]     E --> F   </pre>	<pre> graph LR     A[RANDOMIZATION] --> B[PEB]     A --> C[NFC]     B --> D[NFC+PEB]     B --> E[PEB+NFC]     C --> D     C --> E     D --> F[POST-TRIAL PERIOD]     E --> F   </pre>	POST-TRIAL PERIOD	
Randomization with sequence generator	Block (Medicine): 5 Medicine floors- PEB 5 Medicine floors- NFC  Block (Surgery): 3 Surgery floors- PEB 3 Surgery floors- NFC	Block (Medicine): 5 Medicine floors- PEB+NFC 5 Medicine floors- NFC+PEB  Block (Surgery): 3 Surgery floors- PEB+NFC 3 Surgery floors- NFC+PEB	Observation assessment

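### No floor is untreated in Period I or II, so the primary claim that both interventions improve administration is a before-after result; the plan names no comparator, does not label it as non-randomised, and lists no adjustment for calendar time

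*Combined protocol and SAP*

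**What the plan says.** The Primary hypothesis section states that "Both interventions (PEB and NFC) will improve medication administration (as measured by missed doses") and names no comparator. The direct comparison of PEB with NFC, which is the aim in the title and Overview, appears as secondary hypothesis 3. Secondary hypotheses 1 and 2 predict that the combination will reduce refusals and other missed doses. Secondary hypothesis 8 predicts a fall in VTE events.

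The schedule in the Analysis plan opens with "PRE-TRIAL (6 MONTHS"). In Period I, 5 medicine and 3 surgery floors have PEB, and 5 medicine and 3 surgery floors have NFC. In Period II every floor has both; the medicine row reads "5 Medicine floors- PEB+NFC 5 Medicine floors- NFC+PEB", and the surgery row follows the same pattern with 3 and 3. The schedule closes with "POST-TRIAL (3 MONTHS"), described only as "Observation assessment".

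Two comparisons are planned: "We will compare outcomes across intervention periods" and "We will compare outcomes based upon randomized floor". The covariates are given as "We will adjust by floor type (medicine vs. surgery) and patient level characteristics (race, sex, age, insurance"). No period, month, season or trend term is listed.

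**The concern.** A reader of a cluster randomised trial will take its primary conclusion to be protected by the randomisation. Here it is not. The second intervention is added to the first rather than replacing it, and no floor is left without an intervention during the trial periods. A statement that PEB improves administration, that NFC does, or that the combination does therefore needs a comparison with an earlier time. The only time scheduled before either intervention is the pre-trial block.

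If missed doses were falling across the hospital for unrelated reasons, the fall would be reported as benefit. If they were rising, a real benefit could be hidden. As written, the plan neither warns the reader of this nor includes an analysis that examines it.

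**Working it through.** **1. Count of untreated floors.** From the schedule, Period I has 5 + 3 = 8 floors on PEB and 5 + 3 = 8 on NFC, which gives 16. This reproduces the 16 floors (10 medicine, 6 surgery) under Participants. Untreated floors number 0 of 16 in Period I and 0 of 16 in Period II.

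**2. What can be estimated.** Take a floor-by-period model with 16 floor effects, a free effect for each period after the first, and effects for PEB, NFC and the combination.

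- Pre-trial, I and II: 16 + 2 + 3 = 21 columns. The PEB and NFC columns sum to the Period I column, and the combination column equals the Period II column. These are two dependencies, so the rank is 21 − 2 = 19.
- Adding the post-trial period: 22 columns, rank 20, whether that period is coded as untreated or as still on both.

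In each case PEB, NFC and the combination against no intervention are not estimable, and PEB minus NFC is. This result needs no assumption about drift or variance. The absolute effects become estimable only when the pre-trial block is used and time is either left out (plain before-after) or given an assumed shape such as a straight line.

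**3. Why the randomised contrast is safe.** With a drift d common to all floors, the Period I contrast is (PEB effect + d) − (NFC effect + d), and d cancels. In a simulation of 200,000 replicates under common drift, its rejection rate stayed at 0.049 to 0.051.

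**4. Illustration of drift.** The drift rate, the SD of floor-level change (1 to 2 percentage points, pp) and the use of a paired t-test in place of multiple outputation are all assumptions. Period midpoints are months 3, 7.5 and 10.5, so the gaps from the pre-trial midpoint are 4.5 and 7.5 months. Spurious change = monthly drift × gap:

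| Assumed fall per month | Period I | Period II |
|---|---|---|
| 0.1 pp | 0.1 × 4.5 = 0.45 pp | 0.1 × 7.5 = 0.75 pp |
| 0.2 pp | 0.2 × 4.5 = 0.9 pp | 0.2 × 7.5 = 1.5 pp |

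For one arm of 8 floors, noncentrality = change / (SD/√8), with 7 degrees of freedom and a two-sided 0.05 test. At 0.9 pp this is 0.9/(1/2.83) = 2.55 for SD 1, and 1.27 for SD 2. With no true effect:

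| Period I drift | One arm falsely significant (SD 2 to SD 1) | Both arms falsely favourable (arms independent) |
|---|---|---|
| 0.45 pp | 9% to 20% | 0.6% to 4% |
| 0.9 pp | 20% to 59% | 4% to 35% |

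In the adverse direction, assume a true fall of 2 pp in each arm. Power for both arms is 46% to 99.5% without drift, 22% to 93% with 0.45 pp of adverse drift, and 7% to 58% with 0.9 pp.

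**5. What a linear trend term costs.** The ratios below are standard errors relative to the untrended analysis of 6 + 3 + 3 months, assuming independent monthly errors:

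| Data | Single PEB or NFC step | Average Period I step | Combined step |
|---|---|---|---|
| 6 + 3 + 3 months | 1.41 | 1.70 | 2.50 |
| plus 12 earlier months | 1.03 | 1.11 | 1.23 |

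The term can also add bias when drift is not linear. With no true effect and an assumed 12-month sine of amplitude 0.5 pp, one timing of the cycle raised the false improvement from 0.54 to 0.70 pp in Period I and from 0.71 to 0.97 pp in Period II. With an assumed one-off fall of 0.5 pp midway through the pre-trial block, a false improvement of 0.25 pp became a false worsening of 0.22 pp (Period I) and 0.53 pp (Period II).

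**The case against.** The case on the other side has four parts.

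- **The plan makes no false claim.** It shows the pre-trial column, refers to pre-implementation data, lists the over-time and by-floor comparisons separately, and never calls the improvement a randomised effect. This stands, and it makes the gap one of labelling and comparator. But "We will compare outcomes across intervention periods" is the before-after contrast itself, not an adjustment for time.
- **Randomisation does more than compare PEB with NFC overall.** This stands too. It also supports hypotheses 3a and 3b, moderation of PEB versus NFC (hypotheses 4 to 7), and the Period II comparison of order. None of these is a comparison with no intervention.
- **The evidence for drift is thin.** A reader might infer that missed doses were already changing across the hospital. The documents do not show that. The Background mentions efforts on physician ordering, whereas the outcome is the administration of doses already prescribed. The prior intervention affected some floors, and a sensitivity analysis excludes them. No trend is reported, so the percentages above should carry no weight in judging how serious the point is.
- **A trend model is not a clear improvement.** On this schedule it costs precision, assumes linearity, and can increase bias. It is therefore suitable only as a sensitivity analysis.

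The post-trial months do not settle the matter. The plan does not say whether the interventions continue in them, and any comparison using them would still be non-randomised.

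**Conclusion.** The point holds as a matter of design. With 0 of 16 floors untreated in either trial period, the primary hypothesis and secondary hypotheses 1, 2 and 8 rest on change over time, with an unnamed reference and no listed time term. That conclusion follows from the schedule alone. The size of any resulting error is unknown, and the figures shown depend wholly on assumed drift and variability.

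A reader might go further and infer that the trial's randomisation is wasted, or that PEB versus NFC must become the primary comparison. The documents support neither. The randomised contrast is already planned and is protected against drift common to all floors. Re-ranking is a trade-off: with 8 floors against 8 and an assumed SD of 1 to 2 pp, power for a 1 pp difference is only about 46% to 15%.

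**What to change.** 1. **Comparator and label.** Name the pre-trial period as the reference for improvement. State that the improvement, combination and VTE-decline conclusions will be reported as non-randomised before-after results. The cost is a few sentences.
2. **Randomised result.** Estimate the Period I PEB-versus-NFC contrast adjusted for each floor's pre-trial missed-dose proportion and floor type, and present it as the trial's randomised result. The pre-trial period is already scheduled. Going from 14 to 12 degrees of freedom, with no gain in SD assumed, lowers power for a 1 pp difference only from 0.461 to 0.452 (SD 1) or from 0.154 to 0.152 (SD 2).
3. **Sensitivity analysis only.** Add a monthly floor-level model with a calendar-time trend, reported beside the unadjusted before-after result. State that it assumes linear drift, does not protect against seasonality or step changes, and raises the standard error about 1.4-fold (single step) to 2.5-fold (combined step) on 6 + 3 + 3 months. Use earlier registry months if they exist for these floors; the documents do not say that they do.

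No change to the floors, interventions, schedule or ranking of hypotheses is required.

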**Secondary hypotheses**

1. Combining both interventions (PEB and NFC) will decrease patient refusal of VTE prophylaxis
2. Combining both interventions (PEB and NFC) will decrease missed doses for reasons other than patient refusal

3. Overall, PEB intervention will be more effective than NFC in reducing missed doses for any reason:
  - a. The PEB intervention will be more effective than NFC in reducing in reducing patient refusal
  - b. The NFC intervention will be more effective than PEB in reducing missed doses for other reasons of missed doses other than patient refusal
4. There will be a differential effect on medicine and surgery floors
5. There will be a differential effect by patient level characteristics (race, age, sex)
6. There will be a differential effect on high vs. low performing floors
7. There will be a differential effect dependent on pharmacological dosing regimen (i.e. medication, frequency)
8. There will be an overall decline in the incidence of VTE events (all, DVT, PE)

## **Design**

A single institution, crossover, cluster randomized controlled trial (x-cRCT).

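### The trial is labelled a crossover, but its schedule is a Period I parallel comparison followed by add-on on every floor, so only PEB versus NFC has randomised support

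*Combined protocol and SAP*

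**What the plan says.** The title calls the study "A crossover, cluster randomized controlled trial", and the Design section repeats the label: "A single institution, crossover, cluster randomized controlled trial (x-cRCT". The Participants section also excludes data from a cross-over window.

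The schedule table at the end of the Analysis plan shows something else:

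- **Pre-trial:** 6 months.
- **Period I (3 months):** 5 medicine and 3 surgery floors on PEB; 5 medicine and 3 surgery floors on NFC.
- **Period II (3 months):** every medicine and surgery floor on both interventions, labelled PEB+NFC or NFC+PEB.
- **Post-trial (3 months):** observation. Whether the interventions continue is not stated.

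Secondary hypothesis 1 confirms that Period II is add-on and not a switch: "Combining both interventions (PEB and NFC) will decrease patient refusal of VTE prophylaxis". Hypothesis 2 uses the same construction for the other reasons for missed doses.

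The primary hypothesis is "Both interventions (PEB and NFC) will improve medication administration (as measured by missed doses", with no comparator. Hypothesis 3 is the head-to-head: "Overall, PEB intervention will be more effective than NFC in reducing missed doses for any reason".

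The Analysis plan says "We will compare outcomes across intervention periods" and "We will compare outcomes based upon randomized floor". It does not say which period or contrast tests which hypothesis. The listed adjusters are floor type, race, sex, age and insurance.

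**The concern.** In a two-period crossover each cluster receives each treatment alone, in random order. The treatment comparison is then randomised in both periods and each cluster acts as its own control. This schedule lacks that property. The Period II arms differ only in the order in which the two interventions were introduced.

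The larger issue is the primary hypothesis. No floor is untreated during Periods I and II, and none stays on a single intervention while others have the combination. Any claim that the interventions, or their combination, improve administration must therefore rest on a different calendar period. Under the present label, such a before-after result could be reported as randomised evidence, and a hospital-wide change in missed doses could be read as an intervention effect.

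**Working it through.** **1. Floor counts.** Period I: PEB 5 + 3 = 8, NFC 5 + 3 = 8. Period II: 5 + 5 + 3 + 3 = 16, all on both interventions. The total of 16 matches the Participants section. PEB-alone against NFC-alone is 8 versus 8 in Period I and does not exist in Period II.

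**2. What can be estimated.** Let a₁ and a₂ be the mean levels of the two arms, π₁ and π₂ free effects for Periods I and II relative to pre-trial, and P, N and C the effects of PEB, NFC and the combination.

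| | Pre-trial | Period I | Period II |
|---|---|---|---|
| PEB-first floors | a₁ | a₁ + π₁ + P | a₁ + π₂ + C |
| NFC-first floors | a₂ | a₂ + π₁ + N | a₂ + π₂ + C |

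- π₂ and C occur only as a sum. Adding a constant to π₁ and subtracting it from both P and N changes nothing.
- The design matrix has 7 columns and rank 5. With 16 separate floor effects it is rank 19 of 21.
- P − N is estimable. P, N, their average, C, and C minus either single effect are not.
- Adding the post-trial period as untreated, with its own free effect, gives rank 20 of 22 and does not change this.

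The fault is therefore aliasing. A categorical period term could not separate time from treatment. Only an assumed form for the trend can.

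**3. Possible size of a time effect (illustration).** If the periods of 6, 3 and 3 months run without gaps, their midpoints are months 3, 7.5 and 10.5. Periods I and II then lie 4.5 and 7.5 months after the pre-trial midpoint. The documents give no trend, so a background fall of 0.1 to 0.2 percentage points per month is assumed:

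- Period I: 0.1 × 4.5 = 0.45 to 0.2 × 4.5 = 0.9 points.
- Period II: 0.1 × 7.5 = 0.75 to 0.2 × 7.5 = 1.5 points.

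The only rate in the documents is the Background's "approximately 12% of prescribed doses of pharmacologic VTE prophylaxis were not administered". Against that 12%, these falls are 3.75% to 7.5% and 6.25% to 12.5% in relative terms. The 12% is historical hospital data, not these floors' pre-trial rate.

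**4. Cost of a linear trend assumption.** With equal, independent monthly means per arm and one common linear trend, every contrast becomes estimable. The table gives the SE with the trend divided by the SE without it.

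| Contrast | 12 months (pre-trial, I, II) | 15 months (post-trial untreated, no carry-over) |
|---|---|---|
| PEB − NFC | 1.00 | 1.00 |
| Average single vs no intervention | 1.70 | 1.00 |
| Combination vs no intervention | 2.50 | 1.07 |

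**5. Baseline adjustment of PEB versus NFC in Period I.** Let ρ be the correlation between a floor's pre-trial and Period I rates. With 16 floors in two arms and one covariate, the SE relative to the unadjusted contrast is √[(1 − ρ²) × (1 + 1/12)], where 12 = 16 − 4. The documents do not give ρ.

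| Assumed ρ | 0 | 0.2 | 0.3 | 0.5 | 0.7 | 0.8 |
|---|---|---|---|---|---|---|
| Relative SE | 1.04 | 1.02 | 0.99 | 0.90 | 0.74 | 0.62 |

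Simulation agrees to within about 0.01.

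**The case against.** The schedule discloses the add-on openly, so the label could be called a matter of terminology. That answer covers PEB versus NFC, which remains a valid randomised comparison in Period I. It does not cover the primary and combination hypotheses, where the label implies support that the design cannot give.

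The Analysis plan is also an outline without a model equation, so silence is weak evidence of exclusion. This stands, and it rules out several stronger readings:

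- **That the error is a missing time covariate.** Period is itself one of the planned comparisons, and a free period term would be aliased with treatment. What is missing is a named comparator and a stated trend assumption.
- **That pre-trial floor rates will be ignored.** The plan does not state such an adjustment. It does intend a check involving pre-implementation data and an analysis by high- and low-performing floors. Neither is a floor-baseline adjustment, but both show that baseline data are in view.
- **That Periods I and II will be pooled by randomised arm, diluting PEB versus NFC.** Nothing in the plan says so, and no size should be attached to it.
- **That missed doses are already falling.** No trend is documented in either direction.

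Baseline adjustment is a gain in precision, not the correction of an error, and it brings almost no gain or a slight loss at correlations of 0.3 or below. The post-trial period could also make a trend-based analysis far less costly, as step 4 shows. That depends on the interventions stopping, which is not stated.

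**Conclusion.** The concern holds. The crossover label does not describe the schedule. PEB versus NFC (hypotheses 3, 3a and 3b) has a randomised contrast in Period I only, 8 floors against 8. The primary hypothesis, hypotheses 1-2 and hypothesis 8 are before-after comparisons that cannot be separated from calendar time without a trend assumption, and the plan states none. This conclusion follows from the schedule alone and needs no assumed value.

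The apparent falls of 0.45 to 0.9 points (Period I) and 0.75 to 1.5 points (Period II) are illustrations under an assumed drift and consecutive periods. The SE ratios for the trend rest on equal, independent monthly means. Those for baseline adjustment rest on assumed correlations.

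A reader might infer that the trial cannot answer its title question. The documents do not support that: the head-to-head is randomised and unaffected by a common trend.

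**What to change.** 1. **Relabel the design** as a parallel cluster-randomised comparison (Period I) followed by add-on of the other intervention on all floors (Period II). Reconcile the title, the Design section, the cross-over exclusion under Participants and the schedule table.
2. **Test hypotheses 3, 3a and 3b on the Period I contrast** by randomised arm, adjusted for each floor's pre-trial rate of the same outcome. Treat the Period II between-arm difference as a comparison of order only.
3. **Name the comparator period** for the primary hypothesis and hypotheses 1-2, and do the same for hypothesis 8. Report them as non-randomised before-after comparisons under a stated trend assumption, with a segmented analysis of monthly rates as a sensitivity analysis.
4. **State whether the interventions continue in the post-trial period** and how those 3 months enter the analysis.

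**Cost.** The changes are to wording and analysis specification. They need no new floors and use periods already scheduled. Baseline adjustment risks an SE about 4% larger if the correlation is zero. With 12 months of data, a linear trend raises the SE about 1.7-fold (average single intervention) and 2.5-fold (combination). The crossover label and the claim of randomised evidence for the primary and combination effects are given up.

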## **Participants**

### **Eligibility Criteria**

Participating floors will be assigned one of two interventions based on a randomization sequence.

Eligible floors are defined as:

- A. All medical and surgical floors (non- intensive care units)
- B. 16 total floors (10 medicine, 6 surgery)

Eligible Patients are defined as: All patients on assigned floors except:

- A. Patient data for those transferred between floors will be excluded.
- B. Patient data for those on floors during the cross-over time will be excluded.

